### Specific Aims:

**Aim 1: To determine whether the composite rate of hospital readmissions, emergency department, urgent clinic visits for HF and death are lower in patients with ADHF treated with dapagliflozin compared to those treated with placebo.** Patients with and without diabetes ADHF will be randomized to receive either dapagliflozin (10 mg once daily) or placebo at hospital discharge for 26 weeks.

**Hypothesis:** Treatment with dapagliflozin will significantly reduce the composite rate of hospital admissions, emergency department visits and urgent clinic visits for HF compared to placebo in patients discharged after an ADHF admission.

[figure not shown]
**Aim 2: To determine whether treatment with dapagliflozin compared to placebo will result in lower HF disease-specific biomarker (NT proBNP), improvement in glycemic control (HbA1c) in T2D patients, and improvement in symptoms and quality of life after hospital discharge in patients with ADHF.** We will measure changes in HbA1c, NT proBNP levels and HF-specific quality of life assessment using the Kansas City Cardiomyopathy Questionnaire (KCCQ) and improvement in symptoms using the Chronic Heart Failure Questionnaire (CHQ-SAS).

**Hypothesis:** Treatment with dapagliflozin will result in a greater improvement in HbA1c levels (in T2D patients), HF disease-specific marker (NT proBNP), quality of life (KCCQ scores), improvement of symptoms (CHQ-SAS scores) compared to placebo after hospital discharge at 12 and 26 weeks.

**Aim 3. Evaluate the within-trial cost-effectiveness of dapagliflozin compared to placebo in overall healthcare costs in patients with ADHF.** We will prospectively collect information on overall health care costs including emergency room visits, urgent clinic visits for HF, and hospitalizations between groups during the 6 months of intervention.

**Hypothesis:** Treatment with dapagliflozin will be associated lower resource utilization and health care costs compared to placebo after hospital discharge.

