**Schedule of Assessments:**

Visit		2	3	4	5	6	7	8	9
Screening	Randomization (Discharge) c								
Week	0	0	2	6	8	12	16	20	24
Clinic / CTSA Visit		X	X	X		X		X	X
Phone Visit					X		X		X
Sign Informed Consent	X								
Medical History	X								
Weight, BMI	X	X		X		X		X	X
Physical Exam	X	X		X		X		X	X
Vital Signs	X	X		X		X		X	X
Blood & Urine Sampling a	X	X		X ^		X		X ^	X
Urine Pregnancy Test b	X			X		X		X	X
6-minute Walk Distance			X			X			X
KCCQ Questionnaire		X				X			X
CHQ-SAS Questionnaire		X				X			X
AEs and SAEs		X	X	X	X	X	X	X	X
Electrocardiogram		X d							
Echocardiogram c		X				X			
Review Home BG Testing Results in T2D			X	X	X	X		X	X
Home Urine Ketone Testing, if Indicated			X	X	X	X		X	X
Study Drug Dispensing		X				X			
Study Drug Returned						X			X
T2D Education	X								
Heart Failure Education	X								

aAdmission tests: For screening purposes we will use available laboratory results during current admission (chemistry including eGFR, HbA1c, urine studies), additional testing will be necessary to meet all the baseline lab requirements such as serum magnesium, NT-proBNP, ketones (patients with T2D at investigator's discretion), albumin/creatinine ratio, random urine sodium , at baseline (prior to discharge). Follow up testing at 12 and 26 weeks; other ^blood tests at 6 and 20 weeks and urine culture will be performed at investigator's discretion. bUrine pregnancy test for women with childbearing potential at investigator's discretion c Echocardiogram during hospital admission (or within 6 months prior to index hospitalization) and at 12 weeks follow up visit. All visits have a +/-7-day visit window. d the most current ECG during admission. e Randomization can be performed prior to discharge or up to 7 days after discharge (if discharge planning over the weekend. \*\*COVID-19: For modified study visit options applicable during the time period of the COVID-19 emergency, please see appendix B.

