12. Cost-effectiveness evaluation of resource utilization overall healthcare costs after hospital discharge in patients with ADHF. We propose to conduct an accompanying within-trial cost-effectiveness analysis using observed trial data. We will adopt a healthcare payer perspective for this analysis. The primary outcomes include total costs of trial participants. Per the recommendations of the Second Panel on Cost-Effectiveness in Health and Medicine and of the Consolidated Health Economic Reporting Standards (CHEERS), we will provide an impact inventory table and reporting checklist in our reports.

Data for cost outcomes will be derived from observed trial data based on abstraction of electronic medical record systems.

Costs: All costs will be expressed in uniform currency such as 2020 U.S. dollars. Total costs will include all direct costs associated with clinical care provided, and external health care service utilization (ER visits and hospitalizations). External healthcare service utilization will include routine office visits, after-hour clinic visits, after-hour clinic visits (urgent care), ambulance use, emergency room visits, and hospitalizations. To calculate the total costs of utilization at 6 months, the median prices of each healthcare service will be multiplied by the number of each service use during the trial.

13. Laboratory assessments. Blood and urine samples for determination of clinical chemistry, and NT proBNP levels will be obtained as per Study Plan. Serum magnesium and random urine sodium will be measured at baseline and repeated at 12 and 26 weeks.
14. Treatment Compliance/Adherence
  - e. The administration of study medication will be recorded. All stops of study medication prescribed by the investigator will be recorded. Study personnel will collect/record any decrease in oral agents and insulin dosage, and if the investigator determined to stop any previously used OADs or insulin during the study.
  - f. Missed doses of dapagliflozin or placebo blinded study medication will not be taken. If a dose is missed, the next regularly scheduled dose will be taken and will not be doubled.

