**Cost-Effectiveness Analyses:** The endpoints include healthcare charges, and numbers and incidences of emergency room visits, urgent clinic visits for HF, and hospitalizations. For continuous outcomes (e.g. charges), we will use Wilcoxon rank-sum test to compare them between the two groups. Linear regression or quantile regression will be performed to assess the group difference adjusting for other potential confounders such as baseline utility scores. The Chi-square test will be used to compare categorical outcomes (e.g. categorized frequency of emergence room visits), followed by generalized linear models (e.g. logistic regression model) which adjusts for other potential confounders. To model repeatedly measured cost-related outcomes (e.g. utility scores) over time, repeated measures analyses via linear mixed models or generalized linear mixed model will also be performed to estimate the effect of dapagliflozin, time, and their interaction. Potential covariates such as age, gender, race, insurance, and duration of T2D, along with baseline utility score, will be adjusted. Standard model selection and checking procedures will be applied to ensure the adequacy of the adopted models.

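### Aim 3 as written supports a comparison of costs and utilization, not a cost-effectiveness evaluation: utility scores have no source, diabetes duration is undefined for patients without diabetes, and no effect measure is named

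*Combined protocol and SAP*

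**What the plan says.** Specific Aims, Aim 3, sets out to "Evaluate the within-trial cost-effectiveness of dapagliflozin compared to placebo in overall healthcare costs in patients with ADHF". The data described there are resource data: "We will prospectively collect information on overall health care costs including emergency room visits, urgent clinic visits for HF, and hospitalizations between groups". The Aim 3 hypothesis concerns lower resource use and lower health care costs.

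Measurements During follow-up, item 12, adopts a healthcare payer perspective and states that "The primary outcomes include total costs of trial participants". Each cost is a median unit price times the number of uses of that service over 6 months. The source is also given: "Data for cost outcomes will be derived from observed trial data based on abstraction of electronic medical record systems".

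Statistical Methods, Cost-Effectiveness Analyses, lists healthcare charges, and the numbers and incidences of emergency room visits, urgent HF visits and hospitalizations, as endpoints. Utility scores then appear three times: as an example confounder in the regression of charges, as the only example given for the mixed models ("To model repeatedly measured cost-related outcomes (e.g. utility scores) over time"), and in the covariate list, which ends "duration of T2D, along with baseline utility score, will be adjusted".

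The Schedule of Assessments has two patient-reported instruments, the "KCCQ Questionnaire" and the CHQ-SAS, at randomization, week 12 and the last visit. Randomization and Blinding states that allocation is blocked on diabetes status, with patients without diabetes included.

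**The concern.** Three things in the Aim 3 analysis do not connect to the rest of the plan.

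- **Utility scores.** They are both modelled and adjusted for, but nothing in the schedule or the measurement list produces them.
- **T2D duration.** It is a covariate in a trial that deliberately enrols patients who do not have the disease. There is no coding rule and no restriction to the T2D stratum.
- **No cost–effect link.** The aim is labelled cost-effectiveness, yet costs and visits are compared one at a time and no health effect is set against cost.

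If this stays open, the effect measure, the covariates and the handling of patients without diabetes will be chosen after the data are seen. An adjusted model fitted by software default could silently drop every patient without diabetes. The published Aim 3 result could also carry a label that its analyses do not support.

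**Working it through.** **1. The plan's own figure.** The documents give no number for Aim 3, so the base is the planned sample size. A two-sided chi-square test at alpha 0.05 with 176 per group, 50% against 35% (50% × 0.70), has power 81.5%; the plan states 82%. Allowing for 10% attrition, 176 / 0.90 = 195.6, rounded up to 196 per group, or 392 in total. This agrees with the plan.

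**2. Source of utilities.** What the analysis needs, set beside what the plan collects:

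| Needed | Collected or defined |
|---|---|
| Utility score at baseline and repeatedly | KCCQ: disease-specific health status, 0–100. CHQ-SAS: 16 symptom and emotional-function items on 7-point scales. No preference-based instrument and no mapping to utilities |
| Cost | Median unit price times count (Measurements, item 12); healthcare charges (Cost-Effectiveness Analyses) |
| Health effect to set against cost | None designated |
| Incremental summary (ratio, net benefit or similar) | None named |

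As documented, baseline utility is undefined for all 392 planned patients. The second row also shows a mismatch: charges and priced costs are different quantities, and the plan does not say which is analysed as total cost.

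**3. Patients with no T2D duration.** Number without a value = 392 × (1 − T2D share). The trial's share is not stated. The background gives more than 40% of patients with established HF (Research Objectives) and 45.3% in a Spanish registry (Sample Size and Power Calculations). The range 40–60% is my assumption.

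| Assumed T2D share | No value | Kept in a complete-case fit |
|---|---|---|
| 40% | 392 × 0.600 = 235 | 157 |
| 45.3% | 392 × 0.547 = 214 | 178 |
| 60% | 392 × 0.400 = 157 | 235 |

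On the 352 evaluable patients (2 × 176), the 40% and 60% shares give 352 × 0.60 = 211 and 352 × 0.40 = 141 without a value.

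**4. What such a loss would mean.** For a generic continuous outcome, the standardized difference detectable with 80% power is (1.960 + 0.842) × √(2/n per group). With n = 176 it is 0.30. With n = 176 × 0.40 = 70.4, 176 × 0.453 = 79.7 and 176 × 0.60 = 105.6, it is 0.47, 0.44 and 0.39. Costs are skewed, so this shows only the order of the loss. The fitted model would also describe patients with diabetes only.

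**5. What can be run.** The Wilcoxon test on charges, the chi-square tests on visit categories, and regressions on age, gender, race and insurance need neither utilities nor T2D duration.

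**The case against.** The strongest reply is that most of the section is workable and speaks to Aim 3's own hypothesis, which is about lower utilization and costs. Utility is not in the endpoint list and is introduced twice only as an example. T2D duration is offered as a potential covariate, model selection follows, and no text prescribes complete-case deletion. A coding rule or a T2D-only model would avoid the loss. The economic evaluation is also not among the listed primary or secondary outcomes, and nothing here touches the primary test, safety or sample size.

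Much of this stands. A reader might infer that the whole economic analysis cannot be run, or that more than half the patients will be lost. The documents support neither. The charge and visit comparisons are feasible, and the loss arises only in a model that includes duration and is fitted on complete cases. The counts also rest on borrowed or assumed diabetes shares.

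The reply does not supply a utility. No other repeated cost-related outcome is named for the mixed models, and the covariate list includes baseline utility as something that will be adjusted for. Nor does it turn separate comparisons into a cost-effectiveness result. Visit counts could serve as the effect, but the plan never designates them, and they are themselves a component of total cost.

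A fair warning applies to any remedy based on a ratio. A cost-per-event ratio is hard to interpret when the effect difference is compatible with zero. By the plan's own power table, the primary test would miss significance in 18% of trials at a 50% placebo rate (100 − 82) and in 38% at a 40% rate (100 − 62), even if the assumed effect is true. Recomputing the 40% case at 176 per group gives 66% power, hence 34%.

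**Conclusion.** The point holds in a limited form. The utility mixed model and the baseline-utility adjustment have no data source. T2D duration is undefined for 157–235 of 392 patients under an assumed T2D share of 40–60%, and those patients would be lost only from a complete-case model that includes it. No effect measure or incremental summary is designated, so the analyses compare costs and utilization and stop short of the cost-effectiveness evaluation that Aim 3 announces.

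The conclusion on utilities and on the effect measure comes from reading the sections side by side and needs no numerical assumption. This should be corrected before analysis, but it does not bear on the primary endpoint. T2D duration is the least serious of the three, since a coding decision settles it.

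**What to change.** In Cost-Effectiveness Analyses and Measurements During follow-up, item 12:

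1. Delete utility scores as outcome and covariate, or state the mapping that derives them from an instrument already collected.
2. Replace T2D duration with the diabetes randomization stratum (yes/no). Use duration only in a model restricted to patients with T2D.
3. Make the main Aim 3 result the between-group difference in mean 6-month total cost per patient, with a bootstrap confidence interval. Use the item 12 definition (median unit price times count), and reconcile it with the charges named in the analysis section.
4. Name primary-composite events avoided as the effect. Present the joint difference in cost and effect as a bootstrap cost-effectiveness plane or as net benefit. Resample whole patients, because non-fatal events also drive cost. Report a ratio only if the effect difference is clearly away from zero.
5. If item 4 is not wanted, relabel Aim 3 as a comparison of costs and utilization.

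The cost is a wording change, a little more analysis work and a narrower claim for Aim 3. No new data collection is needed, because the composite and the service counts are already planned.

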## DATA AND SAFETY MONITORING BOARD

An independent Data and Safety Monitoring Board (DSMB) is established and responsible for monitoring the trial according to the protocol to ensure the safety of patients in the trial. During the course of the study, the DSMB will review the cumulative data collected, evaluate the risk/benefit profile. The DSMB plans to meet after every 6 months or after 150 patients are enrolled.

The DSMB would recommend one of the following actions:

1. Continue the study without modification
2. Modify protocol - based on the safety findings may include frequency of safety monitoring, alterations in study procedures. A recommendation on sample size increase/decrease will be considered after the 50% interim efficacy analysis review.
3. Stop the study - because there is overwhelming efficacy or safety concern, i.e., the risks to patients exceed the benefits to be obtained.

## Interim Efficacy Analysis

For this study, one interim efficacy analysis is planned for the purpose of sample size re-estimation after 50% of the enrolled patients (n=196) have completed the 26 weeks of study period and undergone adjudication of the primary composite endpoint. The process of performing this interim efficacy analysis would, by definition, lead to unblinding of patient treatment to the DSMB. The efficacy analysis and sample size re-estimation will be performed by DSMB members and [name] from the School of Public Health.

## **Stopping Due to Overwhelming Evidence of Efficacy**

Group sequential tests would be performed when 70% of randomized patients have a completed follow-up assessment and have their events adjudicated, using the Gamma family alpha spending function (with gamma = -5).

## **Safety**

### **Potential risks associated with dapagliflozin use:**

**Hypoglycemia.** It is possible that following the proposed protocol, T2D patients receiving basal insulin or dapagliflozin alone or in combination with antidiabetic treatment may develop hypoglycemia (< 54 mg/dl). The frequency of hypoglycemia in patients with T2D treated with dapagliflozin is expected to be < 10%. The number of reports of hypoglycemia will be analyzed statistically. For this analysis, hypoglycemia is defined as a capillary and/or laboratory BG <70 mg/dl, and clinically significant hypoglycemia a BG < 54 mg/dl. Severe hypoglycemia is defined as an event with symptoms consistent with hypoglycemia in which the subject required the assistance of another person and blood glucose less than 40 mg/dl.

**Volume depletion.** SGLT2-is, including dapagliflozin may cause intravascular volume contraction. Treatment with SGLT2-i leads to increased diuresis, which may result in a modest reduction in blood pressure. The risk of volume depletion is enhanced when two diuretics are used in combination, especially with the use of loop diuretics. Therefore, the drug should be given with caution in patients with volume depletion and hypotension. In this trial, we will exclude patients with hemodynamic shock with systolic blood pressure <100 mm Hg after initial fluid resuscitation.

**Hypotension.** SGLT2-is, including dapagliflozin may cause natriuresis and intravascular volume contraction that may lead a modest reduction in blood pressure. The risk of hypotension may be higher in elderly patients with renal impairment receiving two diuretics and the use of loop diuretics. In this trial, we will exclude patients with systolic blood pressure <100 mm Hg and during therapy, diuretic and/or antihypertensive drugs may need to be adjusted in patients with blood pressure < 100 mmHg.

**Urinary tract infection.** Dapagliflozin as all of the SGLT2-i are associated with more frequent urinary tract infections compared with placebo. The percentage of diagnosed urinary tract infections in a recent safety analysis was 3.6% for dapagliflozin and 3.7% for placebo. Urinary tract infections were observed in a greater proportion in patients with a history of recurrent urinary tract infection compared with those without a history of recurrent infection. In this trial, patients with a diagnosis of pyelonephritis or recurrent urinary tract infections will be excluded, and symptoms/signs of UTI will be closely monitored during the clinical trial.

**Mycotic genital infection.** The use of SGLT2-i has been associated with increased susceptibility to genital mycotic infections. In the recent DECLARE study (REF), the rate of genital infections that led to discontinuation of the regimen or that were considered to be serious adverse events (0.9% vs. 0.1%, P<0.001). This AE is usually mild in intensity, respond to local/systemic treatment, and rarely result in drug discontinuation. In this trial, patients with recurrent genital mycotic infections will be excluded, and symptoms/signs of mycotic genital infection will be closely monitored during the trial.

**Diabetic ketoacidosis** is a rare complication in patients with T2D reported with the use of SGLT2-i. In the recent DECLARE study, diabetic ketoacidosis was more common with dapagliflozin than with placebo (0.3% vs. 0.1%, P=0.02), as was the rate of genital infections that led to discontinuation of the regimen or that were considered to be serious adverse events (0.9% vs. 0.1%, P<0.001). Patients treated with dapagliflozin who present with signs and symptoms consistent with severe metabolic acidosis will be assessed for ketoacidosis regardless of presenting blood glucose levels, as ketoacidosis associated

with dapagliflozin may be present even if blood glucose levels are less than 250 mg/dL. If ketoacidosis is suspected, the drug should be discontinued, patient should be evaluated, and prompt treatment should be instituted. Treatment of DKA may require insulin, fluid replacement.

**Acute kidney injury and impairment in renal function.** There have been reports of acute kidney injury in patients receiving SGLT2-I. Dapagliflozin should be avoided during prolonged fasting or fluid losses (such as gastrointestinal illness). SGLT2-i may increase serum creatinine and decreases eGFR. Patients with moderate renal impairment (eGFR less than 25 mL/min/1.73 m^2) should not be started on dapagliflozin.

**Lower limb amputation.** An increased risk for lower limb amputation (primarily of the toe) has been observed in clinical studies with SGLT2-I therapy. In the recent DECLARE study, the rate of non-traumatic lower limb amputations was not increased compared to placebo treatment. Patients at increased risk of amputations including such as a history of prior amputation and diabetic foot ulcers will not be enrolled in this trial.

**Changes in serum magnesium.** Recent reports and a meta-analysis of 18 RCTs involving 15,309 patients provided evidence that SGLT2 inhibitors significantly increase serum magnesium levels in patients with T2D. On average, serum magnesium levels were raised by 0.04-0.06 mmol/l for all SGLT2-I agents indicating a drug class effect. The mechanisms are not completely understood, but likely relates to SGLT2 i- induced glucosuria and osmotic diuresis. The significant elevations in serum magnesium levels are not known, with some studies reporting an association between high magnesium levels and total mortality in individuals with heart failure and those receiving hemodialysis. However, in the general population and in people with type 2 diabetes, high end of the normal range of serum magnesium has been associated with a lower risk of cardiovascular events, lower systolic BP by 2.00 mmHg and diastolic BP by 1.78 mmHg compared with placebo. It has been hypothesized that a modest increase in serum magnesium could have contributed to a reduction in cardiovascular mortality observed among participants with type 2 diabetes in the EMPA-REG OUTCOME trial.

